7.4.9.1. Serum Collagen Type I Telopeptide (CTX)

Blood samples will be collected at the Baseline Visit (Day -1) and on Day 7 of each study period. Approximately 1 mL will be collected as a fasting sample from the subject at the start of each of these visits.

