Genetic deletion of TRPV4 in mice has also been shown to alter bone metabolism. Specifically, congenital TRPV4 KO mice displayed impaired bone resorption due to decreased osteoclast number and activity; osteoblast and osteocyte numbers were not affected [Masuyama, 2008; Mizoguchi, 2008; van der Eerden, 2013]. These changes in osteoclast function resulted in increased bone mass and intracortical porosity along with reduced bone elasticity and hind-limb unloading-induced bone loss. Consistent with a role for TRPV4 in modulating osteoclast function, TRPV4 KO mice exhibited altered serum Collagen Type I C-Telopeptide (CTX) and urinary deoxypyridinoline (DPD), specific markers of bone resorption, while no changes in procollagen type 1 amino-terminal propeptide (P1NP), a specific marker of bone formation, were observed. In addition, no differences in serum calcium or parathyroid hormone (PTH) were noted, suggesting no major changes in external calcium balance. Consistent with these latter findings, rats treated for 7 days with the TRPV4 inhibitor GSK2193874 exhibited no changes in plasma calcium or urinary calcium excretion [Thorneloe, 2012]. Osteoclast function, however, has not been assessed in any drug-induced model. As a result of the findings in TRPV4 KO mice, associations between genetic variants in the TRPV4 gene locus with fracture risk were assessed. Whereas risk of osteoporotic fracture was 1.9 times higher in men homozygous for an intronic SNP in the TRPV4 gene (T-allele of rs1861809) in the Rotterdam Study population, these results were not replicated in other

cohorts and no trends were observed for women [van der Eerden, 2013]. In spite of the low risk that GSK2798745 will alter bone metabolism in mature adult patients, fasted serum CTX will be assessed at baseline and on Day 7 of each study period.

Taking into account the measures taken to minimize the risk to subjects participating in this study, including a 30-fold exposure margin from the NOAEL in dogs, the potential risks identified in association with GSK2798745 are justified by the anticipated benefits that may be afforded to subjects with heart failure.

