9.4.2. Secondary Analyses

For other diffusing capacity pharmacodynamic (PD) endpoints such as DLno, D_M and V_c , similar analyses as in Section 9.4.1 will be provided, as data permit. For these PD endpoints, which may be \log_e transformed prior to analysis to satisfy model assumptions, point estimates and their associated 95% confidence intervals will be back-transformed to provide point estimates and 95% confidence intervals for the ratios.

For pulmonary function measurement endpoints such as FVC, FEV1, FEF_{25-75} FEF_{50} , and FEF_{75} , FRC and EELV, similar analysis as in Section 9.4.1 will be provided, as data permit. For these PD endpoints, which may be \log_e transformed prior to analysis to satisfy model assumptions, point estimates and their associated 95% confidence intervals will be back-transformed to provide point estimates and 95% confidence intervals for the ratios.

For respiratory rate measurement and dyspnea score, similar analysis as in Section 9.4.1 will be provided, as data permit.

In terms of DLco and DLno changes from baseline after saline challenge on Day 5 and after exercise on Day 7, the change from baseline for the challenge (after-before) will be calculated and summarized in tabular format by treatment. A statistical analysis will be performed using a mixed effect model with a fixed effect term for treatment, period and sequence, random effect term for subject-within-sequence, and baseline as a covariate, if data permit. Point estimates and associated 95% confidence intervals will be constructed for the differences between the active treatment and placebo.

In terms of ventilatory efficiency, scatter plots for Ve/VCO₂ at Baseline and Day 7 will be performed and the slope or correlation of Ve/VO₂ provided. Summary statistics for Ve and VCO₂ and change from baseline measurement will be provided.

Details on the analysis of other endpoints will be provided in RAP.

Pharmacokinetic analyses will be the responsibility of the Clinical Pharmacology Modeling & Simulation Department within GlaxoSmithKline. Plasma GSK2798745 concentration-time data will be analyzed by non-compartmental methods with the latest available version of WinNonlin software. Calculations will be based on the actual sampling times recorded during the study. From the plasma concentration-time data, the pharmacokinetic parameters such as Cmax and AUC may be determined, as data permit.

The details of the PK analysis will be listed in the RAP.

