1. REPORTING & ANALYSIS PLAN SYNOPSIS

Overview	Key Elements of the RAP
Purpose	
 This RAP details all planned analyses and outputs required for the final Clinical Study Report (CSR) of Study 201881.
Protocol	
 This RAP is based on the protocol amendment 02 (Dated: 19-APR-2016) for Study 201881 [GlaxoSmithKline Document Number: Error! Reference source not found.].
Primary Objective	
 To assess the effect of GSK2798745 on pulmonary gas transfer
Primary Endpoint	
 Change in the diffusing capacity for carbon monoxide (DLco)
Study Design	
 This is a randomized, double-blind, sponsor-unblinded, placebo-controlled, 2X2 crossover study in adults with heart failure. 12 subjects are planned to complete both treatment periods. Additional subjects up to 24 in total maybe needed based on interim decision
Planned Analyses	
 Interim analyses are detailed within Section 4.1 where applicable. All decisions regarding final analysis, as defined in this RAP document, will be made prior to Database Freeze (unblinding) of the study data.
Primary Analysis Population	
 The 'All Subjects' Population is defined as all randomized subjects who receive at least one dose of study medication. The 'Analysis Population' is defined as subjects in the 'All Subjects' population having baseline and post-baseline assessments of the endpoint of interest for both periods. The 'Per Protocol' Population will consist of any 'Analysis Population' subjects who are compliant with protocol-specific criteria. Subjects with specified protocol deviations will be excluded. The 'Pharmacokinetic (PK)' Population is defined as subjects for whom a pharmacokinetic sample was obtained and analysed.
Hypothesis	
 An estimation approach will be used for the comparison between GSK2798745 treatment and placebo for the change from baseline in DLco at Day 4 and Day 7. Point estimates and associated 95% confidence intervals for the differences in means will be constructed to provide a plausible range of values for the true comparisons of interest.

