3.2. Study Objective(s) and Endpoint(s)

Objectives	Endpoints
Primary Objectives	Primary Endpoints

 To assess the effect of GSK2798745 on pulmonary gas transfer 	
 Change in the diffusing capacity for carbon monoxide (DLco)
Secondary Objectives	Secondary Endpoints

 To assess the effect of GSK2798745 on alveolar-capillary conductance (DM) 	
 Change in the diffusing capacity for nitric oxide (DLno), membrane conductance (DM), and capillary blood volume (Vc)

 To assess the effect of GSK2798745 on pulmonary gas transfer following exercise and following an intravenous saline infusion 	
 Change in diffusing capacity for carbon monoxide (DLco)

 To evaluate the effect of GSK2798745 on ventilatory efficiency 	
 Change in the VE/VCO₂ slope determined during a standardized 3-minute step test

 To evaluate the effect of GSK2798745 on pulmonary function 	
 Changes in spirometry measures including forced vital capacity (FVC) and forced expiratory volume in 1 second (FEV1) as well as forced expiratory flows, FEF25-75 FEF50, and FEF75 Change in functional residual capacity (FRC) and end-expiratory lung volume (EELV) measured by body plethysmograph

 To assess the effect of GSK2798745 on dyspnea 	
 Change in dyspnea score

 To assess the effect of GSK2798745 on respiratory rate 	
 Change in respiratory rate continuously measured by body sensor (Preventice Body Guardian)

 To evaluate the safety and tolerability of repeat administration of GSK2798745 	
 Clinical monitoring of vital signs, ECGs, and clinical laboratory safety data, including LFTs and troponin as well as reporting of adverse events (AEs)

 To assess the effect of GSK2798745 on quality of life 	
 Change in SF-36 acute score

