
 • Unscheduled visits will not be included in summary tables or figures, unless otherwise stated. • All unscheduled visits will be listed. 	
Descriptive Summary Statistics	
Continuous Data	Refer to IDSL Statistical Principle 6.06.1
Categorical Data	N, n, frequency, %

Reporting of Pharmacokinetic Concentration	
Descriptive Summary Statistics	Refer to IDSL Statistical Principle 6.06.1 Assign zero NQ values (Refer to GUI_51487 for further details)
Reporting of Pharmacokinetic Parameters	
Descriptive Summary Statistics (Log Transformed Data)	N, n, geometric mean, 95% CI of geometric mean, standard deviation (SD) of logged data and between geometric coefficient of variation (CV _{b/w} (%)): $CV_b (\%) = \sqrt{(\exp(SD^2) - 1)} * 100$ (NOTE: SD is the SD of log transformed data)
Parameters Not Being Log Transformed	tmax, first point, last point and number of points used in the determination of Lambda_λz.
Parameters Not Being Summarised	tmax, first point, last point and number of points used in the determination of Lambda_λz.
Listings	Include the first point, last point and number of points used in the determination of Lambda_λz.
Graphical Displays	

 Refer to IDSL Statistical Principles 7.01 to 7.13. 	

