11.9. Appendix 9: Biomarker A&R Dataset Details

Parameters (BICATCD Code)	Sample	Unit	LLQ	ULQ
Dataset : Biomark (QUEST)				
Adiponectin (ADPN)	Serum	MG/L	2	61
Albumin (ALB)	Urine	MG/L	3	9999
Creatinine (CREAT)	Urine	MMOL/L	0.2	999999.9
C-peptide (MMT) (CPEP)	Serum	NMOL/L	0.1	9999.99
C-Reactive Protein, Highly Sensitive (CRPHS)	Serum	MG/L	0.3.	800
CXCL10 / IP-10 (IP10)	Serum	NG/L	54.5	56000
Fructosamine (FRUC)	Serum	UMOL/L	20	1000
Glucose (MMT) (GLUC)	Plasma	MMOL/L	1.1	277.5
Glucagon (MMT) (No data for IA)	Plasma	N/A	N/A	N/A
Glycohemoglobin A1c (HbA1c)	Whole Blood	MMOL/L	3	18.9
Highly Sensitive Interleukin-6 (IL-6)	Serum	NG/L	0.156	640
Insulin (MMT) (INS)	Serum	PMOL/L	12	99999
Intercellular Adhesion Molecule, Soluble (sICAM)	Serum	NG/L	312	3200000
Matrix Metalloproteinase-9 (MMP-9)	Serum	NG/L	975	40000000
Non-Esterified Fatty Acids (NEFA)	Serum	MMOL/L	0.03	9
Monocyte Chemotactic protein-1 (MCP1)	Urine	NG/L	3.12	800
Plasminogen Activator Inhibitor-1 (PAI-1)	Plasma	NG/L	153	20000000
Resistin (RESIST)	Serum	MCG/L	0.8	800
Dataset : IMGEN (GSK Clinical Immunology)				
Interleukin 18 – Complex (IL18C)	Serum	pg/mL	19.5	N/AP
Interleukin 18 – Free (IL8F)	Serum	pg/mL	4	N/AP

NOTE :

- Urine biomarkers will be reported as ratios to creatinine i.e. Albumin/creatinine (ACR) and MCP-1/creatinine.
- N/A - Not available on DM dataset during RAP completion.
- N/AP = No ranges are normally provided for parameters.

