11.13.11. Non-ICH Listings

Non-ICH Listings					
No.	Population	IDSL / TST ID / Example Shell	Title	Programming Notes	Deliverable [Priority]
Efficacy					
28	All Subjects	Non-Standard EFF_L1	Listing of Gas Diffusion Outcomes (DLco, DLno, Dm, Vc)		SAC [2]
29	All Subjects	Non-Standard EFF_L2	Listing of Gas Diffusion Outcomes Change from Baseline (DLco, DLno, Dm, Vc)		SAC [2]
30	All Subjects	Non-Standard EFF_L1	Listing of VE/VCO ₂	Rows for day -1 and day 7 only	SAC [2]
31	All Subjects	Non-Standard EFF_L2	Listing of VE/VCO ₂ Change from Baseline	Rows for day -1 and day 7 only	SAC [2]
32	All Subjects	PFT9	Listing of Pulmonary Function Test (FVC, FEV1, FEF-25-75, FEF50, FEF75)	Rows for day -1, day 4, and day 7 only	SAC [2]
33	All Subjects	Non-Standard EFF_L2	Listing of Pulmonary Function Test Change from Baseline (FVC, FEV1, FEF-25-75, FEF50, FEF75)	Rows for day -1, day 4, and day 7 only	SAC [2]
34	All Subjects	LB6	Listing of Troponin	(Include change from baseline)	SAC [2]
35	All Subjects	SF6	Listing of SF-36 Acute Score		SAC [2]
36	All Subjects	MOS_S7	Listing of Sleep Study Variables	Include Minimum Oxygen Saturation during sleep, total sleep time, central apnea index, obstructive apnea index, mixed apnea index, hypopnea index, apnea hypopnea index	SAC[2]

[figure not shown]
Non-ICH Listings					
No.	Population	IDSL / TST ID / Example Shell	Title	Programming Notes	Deliverable [Priority]
40	All Subjects	EFF_L2	Listing of Change in Minimum Oxygen Saturation during Polysomnography		SAC[2]
41	All Subjects	EFF_L1	Listing of AUC of HMG-CoA reductase inhibitors and their key metabolites		SAC[2]
37	All Subjects	SF6	Listing of Dyspnea Score	(Include change from baseline)	SAC[2]
PK					
38	PK	PKCL1P	Listing of Plasma GSK2798745 Pharmacokinetic Concentration-Time Data		SAC [2]
39	PK	PKPL1P	Listing of Derived Plasma GSK2798745 Pharmacokinetic Parameters	Include dose and dose number	SAC [2]

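### The SAP plans no output for FRC/EELV, serum CTX or three exploratory endpoints, and leaves out the protocol's pulmonary-function model without declaring it

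*Protocol*

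**What the plan says.** The SAP presents itself as complete. Its synopsis states "This RAP details all planned analyses and outputs required for the final Clinical Study Report", and SAP 3.1 reports no change to the statistical analysis planned in protocol amendment 02. The only amendment logged in SAP section 2 removes the exploratory Bayesian analysis and adds some required displays.

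SAP 3.2 repeats the protocol's secondary endpoint "Change in functional residual capacity (FRC) and end-expiratory lung volume (EELV) measured by body plethysmograph". Protocol 9.4.2 groups these two measures with the spirometry variables and says of them "FRC and EELV, similar analysis as in Section 9.4.1 will be provided, as data permit", where Section 9.4.1 is the mixed model for DLco.

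For the theoretical risk to bone metabolism, Protocol 4.6.1 says "fasted serum CTX will be assessed at baseline and on Day 7 of each study period", and 7.4.9.1 sets the sampling: "Blood samples will be collected at the Baseline Visit (Day -1) and on Day 7 of each study period". Protocol 9.4.3 commits to listing and summarising safety data.

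SAP 3.2 also declares, as exploratory endpoints, changes in plasma and urinary catecholamines, in heart-rate variability from time- and frequency-domain ECG analysis, and in respiratory temporal dynamics during the sleep evaluation.

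The pulmonary-function listing in SAP 11.13.11 is titled "Listing of Pulmonary Function Test (FVC, FEV1, FEF-25-75, FEF50, FEF75" and names nothing else. In SAP 11.4.3, tmax is the first entry in the row headed "Parameters Not Being Summarised".

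**The concern.** Appendix 11 of the SAP is the programming specification. A variable that appears in no overview table, display title or programming note will not be produced by a team that follows it as written. A declared secondary endpoint, the protocol's marker for a named risk and three exploratory endpoints would then be missing from the report, with no stated reason and under a statement that nothing had changed. A reader of the report could not tell whether the data were not collected, not usable or overlooked. The bone-risk question that CTX was added to address would also go unanswered.

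**Working it through.** There is no sample-size or error-rate figure to reproduce. The check sets each declaration beside SAP Tables 3 to 7, Appendices 8 and 9, the display list in Appendix 11 and the mock shells.

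| Variable | Declared or committed in | Where an output would be expected | What is there |
|---|---|---|---|
| FRC, EELV | Protocol 3 and 9.4.2; SAP 3.2 | SAP Table 4; Tables 2.10–2.13; Figures 2.51–2.66; Listings 32–33 | FVC, FEV1, FEF25-75, FEF50, FEF75 only |
| Serum CTX | Protocol 4.6.1, 7.4.9.1, 9.4.3 | SAP Table 5; safety tables; listings; Appendices 8–9 | Nothing; only the schedule and footnote in SAP Appendix 2 |
| Catecholamines | Protocol 3; SAP 3.2 | Sleep listings 36 and 40; Appendix 9 | Nothing; Listing 36 covers oxygen saturation, sleep time and apnea/hypopnea indices |
| Heart-rate variability | Protocol 3; SAP 3.2 | ECG Tables 3.19–3.21; Listing 24 | ECG findings, QTc and conventional ECG values |
| Respiratory temporal dynamics | Protocol 3; SAP 3.2 | Listing 36 | Nothing |

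Counts:

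- Pulmonary-function measures: 7 declared, 5 with output; 7 − 5 = 2 with none (FRC, EELV).
- Exploratory endpoints: 7 declared, 4 with a listing (minimum oxygen saturation, AHI, apnea indices, statin AUC); 7 − 4 = 3 with none.
- Serum CTX: 2 visits × 2 periods = 4 scheduled samples per subject, 0 displays.

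CTX is not covered by the clinical chemistry tables. Protocol Table 3 places it among biomarkers and other assessments rather than clinical chemistry, and the chemistry panel in SAP Appendix 8 does not include it. Other risk-specific checks do have listings: C-SSRS, SNAQ, audiometry and faecal occult blood (Listings 15 to 18).

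Two exploratory objectives have no output for their only declared endpoint: sympathoadrenal activity (catecholamines) and electrocardiographic parameters (heart-rate variability). The pulmonary-function objective is only partly affected, because five spirometry measures remain.

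**Modelling.** Protocol 9.4.2 promises an analysis like that for DLco for all 7 pulmonary-function measures. In SAP Table 4 the statistical-analysis columns are blank for FVC, FEV1 and the three FEF measures, and FRC and EELV have no row. The protocol plans 7; the SAP plans 0. Figure 2.66 is a forest plot of mean changes, but no model is specified for it. SAP 3.1 does not record this difference.

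**tmax.** SAP Table 7 derives it, Table 6 plans an untransformed summary and a listing of derived parameters, Table 4.03 summarises derived parameters without naming an exclusion, and Listing 39 lists them. The exclusion row in SAP 11.4.3 contradicts Table 4.03.

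**The case against.** Several counter-arguments are fair.

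- **The protocol's promise is qualified.** It applies only as data permit, so the sponsor may have had a reason. But the SAP gives none for FRC and EELV, whereas SAP 9.1.1 does say that one site could not collect DLno, DM and Vc. The qualifier allows an omission; it does not record one.
- **SAP 3.1 concerns analyses that the protocol specified.** This stands in part. The conflict with 3.1 is plain for FRC/EELV and the pulmonary-function model. CTX falls under the general commitment in Protocol 9.4.3, and respiratory temporal dynamics and catecholamines at most under the descriptive commitment for the sleep sub-study in 9.4.4. Protocol section 9 names no analysis for heart-rate variability. For the exploratory items, the firmer contradiction is between SAP 3.2 and SAP Appendix 11.
- **Displays may exist that are not shown.** SAP 11.13.1 reserves efficacy tables 2.01 to 2.32 but entries stop at 2.20, and Table 4.04 and Listing 27 have no entry. Unlisted displays cannot be fully excluded. Still, no overview table names the missing variables.
- **tmax is not unreported.** A reader might infer that a PK endpoint has been dropped. The documents do not support that: Listing 39 covers it, Table 4.03 arguably does too, and the exclusion row repeats the contents of the row on log transformation above it, which suggests a copying slip.
- **Appendix 9 is cosmetic.** It lists markers such as "Adiponectin (ADPN") that Protocol Table 3 does not include. This looks like template carry-over. No display in Appendix 11 uses them, so no reported result changes.

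**Conclusion.** The gap is real. As written, the SAP leaves one secondary endpoint bullet (FRC and EELV), the bone-risk marker and three exploratory endpoints without any output. It also omits the protocol's model for all pulmonary-function measures, without declaring the change. It should be corrected, but it does not touch the primary DLco comparison. The conclusion assumes that Appendix 11 and the overview tables are the full display specification, as the synopsis says.

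A reader might go further and infer selective reporting. The documents do not support that: nothing links the omissions to results, and the SAP openly discloses the decision to stop this programme. A reader might also count three unreported secondary endpoints by splitting FRC from EELV and adding tmax. FRC and EELV form one declared endpoint, and tmax has an output. NT-proBNP is collected and has no display either, but it is not a declared endpoint, so its absence breaks no commitment to report an endpoint.

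**What to change.** - Add FRC and EELV to Tables 2.10 to 2.13 and Listings 32 and 33.
- Add for serum CTX a by-treatment summary of Day -1, Day 7 and change, and a listing.
- Add listings for catecholamines, heart-rate variability and respiratory temporal dynamics.
- Either run the Protocol 9.4.2 model for the pulmonary-function measures or record its removal in SAP 3.1. FRC and EELV cannot simply be added to an existing SAP model, because the SAP has none for this group.
- Record in SAP 3.1 any other output that is deliberately dropped, with its reason.
- Reconcile the tmax row in SAP 11.4.3 with Table 4.03 by giving median and range.

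A summary of NT-proBNP is optional, and correcting the Appendix 9 list is tidying. The cost is a few displays from data the protocol already schedules, or a few sentences in SAP 3.1. No new data collection is needed.

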7.4.9.2. Fecal Occult Blood Test (FOBT)

Based on the gastric erosions found in a preclinical model (dogs at ≥ 3 mg/kg), FOBT will be performed to assess any possible drug-related GI blood loss. Due to concomitant anti-platelet therapy that many patients with heart failure receive, along with the common incidence of intestinal mucosal edema and associated diarrhea, findings of fecal blood would not be unexpected in this population. Subjects will be tested for the presence of fecal occult blood prior to the start of treatment period I (between Screening and Baseline) and after each of the two treatment periods.

Once subjects have signed the consent form and have been enrolled into the study based on meeting the eligibility criteria, they will be provided 3 FOBT cards at the end of the screening visit. Study staff will provide the subjects with instructions for completing the tests and subsequent shipment of the tests back to the laboratory. This assessment will be completed between Screening and Baseline (Day -1). Additionally, subjects will be provided 3 FOBT cards on Day 7 of each treatment period with the same instructions for completion and shipment for laboratory analysis.

7.4.10. Suicidal Risk Monitoring

Based on preclinical studies that have been conducted GSK2798745 is considered to be a central nervous system (CNS)-active drug. There has been some concern that some CNS-active drugs may be associated with an increased risk of suicidal thinking or behaviour when given to some patients with certain conditions. Although this drug has not been shown to be associated with an increased risk of suicidal thinking or behaviour when given to this patient population, GSK considers it important to monitor for such events before or during clinical studies with compounds such as this.

Subjects being treated with GSK2798745 should be assessed and monitored appropriately for suicidality and unusual changes in behaviour. Consideration should be given to discontinuing GSK2798745 in subjects who experience signs of suicidal ideation or behaviour.

The C-SSRS is a measure of suicidal ideation and behavior, with demonstrated predictive validity and reliability. Improved assessments of suicidal ideation and behavior are necessary to better understand the relationship between suicidal AEs and medication treatment. The FDA recommends the use of suicidality assessment instruments that map

to the Columbia Classification Algorithm for Suicide Assessment (C-CASA). One such instrument is the C-SSRS. Sections of the C-SSRS include suicidal ideation, intensity of ideation, suicidal behavior, and actual suicide attempt(s). The C-SSRS assesses lifetime and current suicidal thoughts and behaviors across these categories based on an increasing severity of a 1- to 5-rating scale. The semi-structured questionnaire is completed by a trained and experienced neurologist, psychiatrist, or neuropsychologist, or another trained and experienced person approved by the Sponsor, who may be the Principal Investigator or a sub-investigator for the study. See [Appendix 7](#) and the SRM for details of the scale.

